1. INTRODUCTION

Drug-drug interaction (DDI) occurs when one drug (perpetrator drug) varies the plasma concentration and the biological outcomes of the second drug (victim drug). Pharmacokinetic drug-drug interaction (PK-DDI) may occur at the level of absorption, distribution, metabolism, or excretion when a co-exposed drug may result in alteration of blood-concentration vs. times profile of one or both drugs. Induction of CYP450 enzymes by the co-administered drug results in a decrease in substrate drug concentration leading to in-efficacy or inhibition of CYP450 enzymes by another drug resulting in prolonged half-lives and/or higher substrate drug concentration that may enhance the potential for side effects. Drug transporters also play a vital role in drug disposition when both co-exposed drugs have an affinity for the same binding site of the transporter, while age, gender, nutritional status, various diseases, genetic polymorphisms, and ontogeny of the metabolic enzyme may also affect the drug metabolism (**Müller and Fromm, 2011, Michalets, 1998**).

Voriconazole is synthetically derived from fluconazole antifungal. Voriconazole (**Fig. 1**), chemically is ([2R, 3S]-2- [2, 4-difluorophenyl]-3-[5-fluoro-4pyrimidinyl]-1- [1 H -1, 2, 4-triazole-1-yl]-2-butanol) and has a broad spectrum categorized as second-generation triazole antifungal. Voriconazole is also called a 14-alpha-sterol demethylase inhibitor, broadly used to manage invasive Aspergillosis and other serious fungal infections. Voriconazole binds to the rate-limiting enzyme and inhibits the CYP450 enzyme, leading to inhibition of ergosterol synthesis and deposition of 14-alpha-methyl sterols such as lanosterol, so the structure of fungi cell membrane disrupts. Voriconazole is a strong inhibitor of CYP51 (fungal CYP enzyme) as compared to fluconazole. It has additional activity against *Candida Albicans*, *Candida kurusei* *Scedosporium*, *Fusarium*, and certain other emerging pathogens. Usually, the first oral administered dose of voriconazole is 400mg, followed by a maintenance dose of 200mg at a 12hr dosing interval, and in some conditions, the loading dose is maintained at 9mg/kg, twice a day (BD). Voriconazole is rapidly absorbed and has mostly 96% oral bioavailability. The Peak plasma concentration (C_{max}) of voriconazole is 5.27mg/L at 400mg and the

target is achieved in 1-2hr after drug administration. Both C_{max} and AUC are dose-proportional over the range of (200mg-400mg). The volume of distribution is 4.6L/Kg and plasma protein binding is 58%. Terminal elimination half-life ($t_{1/2}$) ranged from 8hr to 15hr and there is no effect over the steady- pharmacokinetics of voriconazole by variation in the timings of administration of dose (morning or evening). Voriconazole is highly metabolized by the hepatic enzyme CYP2C19 and forms a voriconazole-N-oxide as a major inactive metabolite, which has only minimal antifungal activity. Other metabolites also formed such as hydroxyl voriconazole and dihydroxy-voriconazole. Voriconazole shows first pass by enzymes present in enterocytes as well as hepatocytes and major systemic metabolisms occur by cytochrome-P450 enzymes such as CYP2C19, CYP2C9, CYP3A4, CYP3A5, and the 25% metabolism occurs by Flavin containing mono-oxygenase FMO-1 and FMO-3. Renal and Biliary excretion of voriconazole (metabolized form) is about 75%-80% and 20%-25% respectively, whereas, the remaining 2% is excreted in urine as unchanged form. Voriconazole is a potent inhibitor of CYP2C19, CYP2C9, CYP2B6, and CYP3A4 enzymes, present in hepatocytes as well as enterocytes. Voriconazole is a p-glycoprotein (ABCB1) substrate at different levels (intestinal, hepatic, and renal levels) and also it is a weak inhibitor of this transporter. Being a lipophilic drug, Voriconazole would be in the un-ionized form as the pH of the formulation shifts towards a neutral value resulting in enhanced permeation (**Mohanty et al., 2013, Vanhove et al., 2017, Mikus et al., 2011, Herbrecht, 2004**).

Clarithromycin (6-O-Methylerythromycin) is a semi-synthetic macrolide antibacterial agent with a 14-membered ring. The oral bioavailability of clarithromycin parent drug is 52-53% and terminal elimination half-life ($t_{1/2}$) is 8hr (**Logan et al., 1994**). The usually recommended dose in adults of Clarithromycin is 250mg-500mg (P/O) twice a day for 7-14 days in various conditions and in some conditions are also given a single dose of 1000mg. About 53% of a single dose of clarithromycin is excreted in the urine and 40% in feces. The volume of distribution of clarithromycin is estimated to be 191 to 309L and plasma protein binding ranges from 42-72%. Clarithromycin is extensively metabolized by hepatic CYP3A4 and

forms a 14-R-hydroxyclearithromycin active metabolite and inactive metabolite N-desmethyl-clarithromycin (**Rodvold, 1999**). Clarithromycin is an intense inhibitor of CYP3A4 and has the average inhibitory activity of CYP2C19, CYP2D6, and CYP1A2 enzymes at hepatic as well as the intestinal levels (**Furuta et al., 1999, Michalets, 1998**).

At different levels (intestinal, hepatic, and renal levels), several transporters (ABCB1, ABCC2, OATP2B1, and OATP1A2) are substrates of clarithromycin (**Müller and Fromm, 2011**). Voriconazole is an inhibitor of several transporters like breast cancer resistance protein (BCRP), p-glycoprotein, multidrug resistance-associated protein (MRP-1, MRP-2, MRP-4, and MRP-5), and bile salt export pump (BSEP), but exhibited an inhibitory activity of less than 60% (**Lempers et al., 2016, Mikus et al., 2011**). Clarithromycin is also an inhibitor of p-glycoprotein at enterocytes (luminal), hepatocytes (canalicular), and renal (luminal) sites as well as an inhibitor of OATP1B1 and OATP1B3 at hepatocytes (sinusoidal) and intestinal level (**Müller and Fromm, 2011**). Strong inhibitory (IC_{50}) activity of OATP4C1 has also been observed by clarithromycin at intestinal and renal sites (**Sato et al., 2017**). Clarithromycin is a potent inhibitor of the taurocholate uptake in rat OATP1A5-transfected Madin-Darby canine kidney cells, the nearest analog to human OATP1A2 (**Garver et al., 2008**). According to the BCS classification, voriconazole and clarithromycin both are class-II drugs (**Kumar et al., 2014, Kristin et al., 2017**). Nature and pKa of both interacting drugs (i.e., clarithromycin weakly basic in nature with 8.76 pKa and voriz exhibiting both sets of pKa values i.e., basic: 1.76 pKa as well as acidic pKa values: 4.36 and 12.7) make these drugs better candidates for possible potential PK-DDIs.

Keeping in view the nature of voriconazole and clarithromycin a pharmacokinetic drug-drug interaction may likely be possible.

[figure not shown]

Fig.1: Chemical structure of voriconazole

2. OBJECTIVES

The main objectives of this study will be

1. To develop a sophisticated, robust, and sensitive quantification method using HPLC for the determination of voriconazole in biological fluids.
2. To measure the pharmacokinetic parameters [i.e., C_{max} , T_{max} , $T_{1/2}$, AUC, etc.] of voriconazole in healthy volunteers of Pakistan.
3. To evaluate the PK-DDI of voriconazole with clarithromycin and to study the impact of clarithromycin co-administration on the pharmacokinetic parameters of voriconazole.
4. To interpret the data statistically.

3. LITERATURE REVIEW

Co-administration of a precipitant drug with an object drug may alter the object drug's response in the patient. Some drug interactions are clinically significant and beneficial, so it is desirable to use their simultaneous administration for better therapeutic response and reduced potential ADRs. The majority of drug interactions are not clinically significant and may be detrimental resulting in adverse events. Voriconazole's drug interactions can be categorized into: contraindicated, needing dose adjustment, monitoring levels, and no adjustment required (**Herbrecht, 2004**). Many DDI of voriconazole is well documented in the

literature. Purkins and his co-workers performed an open-label, randomized, and cross-over study on 12 healthy volunteers. Effect of cimetidine on pharmacokinetic parameters of voriconazole has been evaluated and an insignificant increase in AUC and C_{max} of voriconazole has been observed, so only monitoring the voriconazole concentration in the body in long term use for toxicity is sufficient (**Purkins et al., 2003b**). Another study is conducted on voriconazole and ritonavir, in which a serious DDI has been reported. C_{max} of voriconazole is decreased by 150% because ritonavir is (CYP2C19 and CYP2C9) enzyme inducer, so an alternative therapy or contraindication along with ritonavir (400mg BID) has been suggested (**Liu et al., 2007**).

Drug interaction of voriconazole with phenytoin has also been reported in the literature. The AUC and C_{max} of voriconazole decreased by 150% because phenytoin is a (CYP2C19 and CYP2C9) enzymes inducer so increased maintenance dose and TDM of voriconazole have been recommended (**Purkins et al., 2003a**). Andrew and his fellow researchers have performed a DDI study of voriconazole with ethinyloestradiol and norethindrone. This study reported increased AUC and C_{max} of voriconazole by 100% because ethinyloestradiol is a CYP2C19 enzyme inhibitor. They have reported that this one is significant interaction and concurrent use of voriconazole, ethinyloestradiol, and norethindrone medications are well-tolerated (**Andrews et al., 2008**). The effect of efavirenz on voriconazole pharmacokinetics has also been studied. This study reported a decrease in AUC by 150% because efavirenz is CYP2C19 and CYP2C9 enzymes inducer (**Damle et al., 2008**).

In recent research conducted on voriconazole with flucloxacillin co-administration in patients having chronic granulomatous disease and influenza-associated aspergillosis, a decrease in plasma voriconazole concentration has been reported. Flucloxacillin induced CYP3A4 enzyme resulting in decreased C_{max} . In this study, the researchers have suggested close monitoring of plasma concentration of voriconazole and avoidance of the combination if possible (**Muilwijk et al., 2017**). A case study of pulmonary aspergillosis patients reported a decrease in voriconazole plasma concentration by co-administration with darunavir (non-

peptidic HIV protease inhibitor). This study report suggested that voriconazole, ritonavir, and darunavir should be given cautiously or combination is avoided **(Becker et al., 2015)**.

Many DDIs occur because voriconazole has variable and non-linear pharmacokinetic behavior. Voriconazole is a CYP2C19 and CYP3A4 enzymes inhibitor as well as a substrate of these enzymes. Enzyme CYP2C19 has genetic polymorphism: poor, moderate, and extensive metabolizers **(Bahar et al., 2017)**. Asian peoples are mostly poor CYP2C19 metabolizers so DDI may be possible in this region and voriconazole may show variable C_{max} because of non-linearity **(Mikus et al., 2011)**. Clarithromycin is CYP3A4 and CYP2C19 enzymes inhibitor and voriconazole are also a substrate and inhibitor of these two enzymes **(Furuta et al., 1999)**. Both drugs share the same enzyme pathway so DDI may be possible. To our knowledge, no work has been done for the evaluation of the effect of clarithromycin on pharmacokinetic parameters of voriconazole to date.

4. METHODOLOGY

This study will be designed in the following three steps.

Step-1: Development of Quantification Method and Its Validation

In the first phase of the current study, we will develop an HPLC method and validation according to standard guidelines for the quantification of voriconazole in a biological matrix. The first phase of the study will comprise of development and validation of the HPLC method for the identification as well as determination of voriconazole in biological fluids.

Step-2: Evaluation of Pharmacokinetic Drug-Drug Interaction

During the second step, sample collection will be carried out and blood samples will be collected in EDTA or heparinized tubes from the enrolled human volunteers, administered with voriconazole alone or co-administered with clarithromycin at specified periods. Further processing of the sample will be done for extractions and subsequent analysis with the developed analytical method. Evaluation of possible pharmacokinetic drug-drug interaction will be carried out through a comparison of pharmacokinetic parameters.

Study Design and Subject

A study designed for drug interaction will be a single oral dose, open-label, randomized, cross-over study of healthy volunteers. The ethical approval of the protocol will be taken from the local ethical committee of the Pharmacy department, Abdul Wali Khan University, Mardan before initiation. This study will follow the “*ethical principles of the Helsinki declaration for medical research involving human subjects*” and “*good clinical practice guidelines*”. Written consent will be obtained from all included volunteers in the DDI study. The study will be comprised of two treatment sequences with a two-week washout period i.e., given in Table-I;

Sequence	Treatment-1 Group-I (n= 12)	Treatment-2 Group- II (n = 12)
Sequence-1	Voriconazole alone (Vfend® Oral Two Tab, strength of 200mg)	Voriconazole + clarithromycin (Vfend® Oral Two Tab, Strength of 200mg with klaricid® Oral Tab, Strength of 500mg)
Two Week Washout Period		
	Treatment-2	Treatment-1
Sequence-2	Voriconazole + clarithromycin (Vfend® Oral sTwo Tab, strength of 200mg with klaricid® Oral Tab, Strength of 500mg)	Voriconazole alone (Vfend® Oral Two Tab, Strength of 200mg)

Table-1: Two Treatment Sequence, Open Labeled, Cross-Over Study Design for the Pharmacokinetic DDI-Study of Voriconazole with Clarithromycin

Inclusion Criteria

Male Pakistani volunteers in good health aged 18-35 years will be enrolled as participants in this study. The selection will be based on: a complete detailed medical

history, clinical examination, voriconazole hypersensitivity test, and evaluation of various biochemical tests like Blood Glucose Level, Hemoglobin (Hb) Level, Serum Glutamic-Pyruvic Transaminase (SGPT) Or Alanine Amino Transferase and Aspartate (ALT and AST, respectively) Level, Urine Test, BUN Level, Albumin to Creatinine Ratio (ACR) Test, Glomerular Filtration Rate (GFR) Level, etc.

Exclusion Criteria

Those volunteers who have a history of voriconazole hypersensitivity reaction, deviation from normal values in the biochemical test report, having any pathology like chronic renal disease, hepatic impairment, and having any cardiovascular, gastrointestinal tract, hematopoietic disorders will be excluded from the study. Alcohol addicted, smokers and volunteers who cannot sign the permission consent form will be excluded from the study.

Collection of Blood-Samples

Blood samples (approximately 3cc) will be collected from overnight fasting inducted volunteers in heparinized tubes at specific time intervals of 0.0 (pre-dose), 0.5, 1.0, 1.5, 2.0, 2.5, 3.0, 4.0, 6.0, 8.0, 12 and 24 hours after administration of two tablets of voriconazole (200mg) either alone or co-administration with clarithromycin (500mg). After taking blood samples, immediately these samples will be centrifuged to separate plasma from blood (RBC) and will be stored at -80°C until analysis.

Samples Analysis

We will develop an RP-HPLC/UV-Vis method for the measurement of voriconazole concentration in biological fluid. The stored samples will be brought back to room temperature by thawing technique and the drug will be extracted from plasma samples with already established extraction solvents and subsequently analyzed with the developed method.

Step-3: Data Assessment and Analysis

In this phase, pharmacokinetic parameters used for PK-DDI assessment will be analyzed statistically using compartment and/or non-compartmental approaches. Assorted pharmacokinetic parameters like C_{max} ($\mu\text{g/ml}$), T_{max} (hrs), $T_{1/2}$ (hrs), $[\text{AUC}]_{0-t}$ ($\mu\text{g.h/ml}$), AUMC ($\mu\text{g.h/ml}$), MRT (hrs), and V_d (L) will be determined

from plasma drug concentration Vs. time profile. All pharmacokinetic parameters will be evaluated using different pharmacokinetic software like PK-Summit® etc., and for graphical data analysis MS-Excel, Minitab, etc. will be used. Appropriate statistical tests like t-test and analysis of variance (ANOVA) will be performed and data will be presented graphically.

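### Does giving clarithromycin only once leave the interaction objective unanswered?

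*Combined protocol and SAP*

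**What the plan says.** All references are to the combined protocol and SAP.

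- **Section 2, Objective 3:** "To evaluate the PK-DDI of voriconazole with clarithromycin and to study the impact of clarithromycin co-administration on the pharmacokinetic parameters of voriconazole". It has no single-dose or repeated-dose qualifier.
- **Section 4, Study Design and Subject:** "A study designed for drug interaction will be a single oral dose, open-label, randomized, cross-over study of healthy volunteers". Table 1 lists the combination as two 200 mg voriconazole tablets with "klaricid® Oral Tab, Strength of 500mg". No tablet count is printed for clarithromycin.
- **Section 4, Collection of Blood-Samples:** voriconazole is given "either alone or co-administration with clarithromycin (500mg" mg), which supports reading Table 1 as one tablet. No pre-treatment or repeat dose is described.
- **Section 1, on clarithromycin:** "The usually recommended dose in adults of Clarithromycin is 250mg-500mg (P/O) twice a day for 7-14 days in various conditions". The same sentence adds that patients "in some conditions are also given a single dose of 1000mg". The half-life entry reads "terminal elimination half-life ($t_{1/2}$) is 8hr".
- **Section 4, Step 3:** the t-test and ANOVA are named. There is no no-effect margin, no rule for reading a null result and no pre-worded conclusion.

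**The concern.** The objective is broad and the experiment is narrow. A reader who sets Objective 3 beside the Introduction could expect evidence about clarithromycin as it is usually taken: twice daily for 7-14 days, or 14 to 28 doses. The trial gives one dose.

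If the ratio of voriconazole exposure with and without clarithromycin came out near 1, it might be reported as showing that the two drugs do not interact. The protocol expects inhibition, so that mistake would leave raised voriconazole exposure unrecognised under repeated dosing. Narrowing the objective, and stating beforehand that a null result does not extend to repeated dosing, would cost only a few words.

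**Working it through.** The plan gives no power, effect size, variability or margin, so it has no figure to reproduce. The check has three parts: how far the trial's clarithromycin exposure differs from the regimens in the Introduction, whether the passages conflict, and what a null result could mean.

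**Inputs**
- Clarithromycin half-life 8 h; regimens of 250-500 mg every 12 h, or 1000 mg once (Section 1).
- Trial dose 500 mg once (Section 4).
- Voriconazole half-life 8 to 15 h, peak at 1-2 h (Section 1).
- Assumed: linear one-compartment kinetics and, for peaks, instant absorption.

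**1. Accumulation on 12-hourly dosing**

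1/(1 − 2^(−12/8)) = 1/(1 − 0.354) = 1.55.

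**2. Exposure over 24 h, relative to the trial**

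The trial's 0-24 h exposure is 1 − 2^(−24/8) = 0.875 of the total AUC from one 500 mg dose.
- 500 mg twice daily at steady state: 2/0.875 = 2.29 times.
- 250 mg twice daily at steady state: (2 × 0.5)/0.875 = 1.14 times.
- 1000 mg once: 2.0 times.

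**3. Exposure over the first 12 h, and peak**

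The trial's 0-12 h exposure is 1 − 2^(−12/8) = 0.646 of the total AUC from one 500 mg dose.
- 250 mg twice daily gives 0.5 on the same scale, so the trial is 0.646/0.5 = 1.29 times **higher**.
- The 250 mg twice-daily steady-state peak is 0.5 × 1.55 = 0.77 of the trial's peak.
- 500 mg twice daily gives 1/0.646 = 1.55 times the trial's 0-12 h exposure.

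The trial's inhibitor exposure is therefore not uniformly lower than usual use. Against the lower end of the stated range it is higher in the window around the voriconazole peak. Nine of the eleven post-dose samples fall within 8 h.

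**4. Does inhibition fade while voriconazole is still present?**

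At 24 h, 2^(−24/8) = 12.5% of clarithromycin remains. For voriconazole the figure is 12.5% at an 8 h half-life and 2^(−24/15) = 33% at 15 h. The two drugs decline together at the lower half-life, and a gap appears only towards the upper one. The Literature Review also calls voriconazole non-linear, so these single-exponential figures are rough.

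**5. Do the passages conflict?**

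| Place | What it fixes |
|---|---|
| Introduction | Therapeutic background, including one single-dose use |
| Objective 3 | Effect of co-administration on voriconazole parameters |
| Study Design, Table 1, blood sampling | Single-dose co-administration |

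Objective 3 does not refer to the 7-14 day course. The Methodology makes a general objective specific, and its parts agree with each other.

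**6. What a null result could mean**

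Take 12 per group as N = 24. On the log scale, SE = s_w·√(2/24) with s_w = √ln(1 + CV²), 22 degrees of freedom and a two-sided 5% t-test. The within-subject CV is assumed, because none is given.

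| CV | Power for a 1.25-fold change | Ratio detectable with 80% power |
|---|---|---|
| 20% | 96% | 1.18 |
| 30% | 71% | 1.28 |
| 40% | 48% | 1.39 |
| 50% | 35% | 1.49 |

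A non-significant result may be inconclusive even for the single-dose question. Rewording Objective 3 would alter none of these values.

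**The case for a change.** The best argument for a change is that the protocol itself reads other work loosely. Its Literature Review takes a non-significant cimetidine effect in 12 volunteers and draws advice about long-term use from it. It also says that no earlier work exists on this pair, so this trial's conclusion could stand alone. It calls voriconazole pharmacokinetics variable and non-linear, which weakens any extrapolation from one dose to many. The trial's 24 h clarithromycin exposure is below all the regimens the Introduction mentions, though only slightly for 250 mg twice daily.

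Much of this stands. A null single-dose result would not exclude an interaction under repeated dosing, and a careful author would put single-dose into the objective. But this is a forecast about reporting. The plan draws no such conclusion about its own result, and any competent report will describe the regimen actually given. The exposure ratios cannot be turned into a bias in the voriconazole ratio either, because the documents give no relation between clarithromycin level and inhibition and do not say whether inhibition grows with repeated dosing. The missing margin and confidence-interval plan is a separate matter, which a qualifier on Objective 3 would not mend.

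**Conclusion.** No change to the plan follows. The scope of Objective 3 is looser than the design, but the design is stated openly, its parts agree, and the within-subject comparison of voriconazole with and without one 500 mg clarithromycin dose answers the co-administration question as posed. Adding a qualifier would leave every dose, sample, estimate and test as it is.

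The difference in clarithromycin exposure is real but mixed: from 1.14 to 2.29 times the trial's over 24 h, yet only 0.77 of the trial's over the first 12 h on 250 mg twice daily (0.5/0.646). These figures rest on linear kinetics and the protocol's 8 h half-life, and they say nothing direct about the size of the interaction. The conclusion also rests on reading Table 1 as one clarithromycin tablet, which the blood-sampling text supports. What remains is ordinary care in reporting: describe the result as the effect of single-dose co-administration, and do not present a null as absence of interaction under repeated dosing.

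### Does Table-1's use of 'Sequence' for what are really the two periods make the design, total N or ANOVA wrong?

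*Combined protocol and SAP*

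**What the plan says.** Section 4, Study Design and Subject, describes a "single oral dose, open-label, randomized, cross-over study of healthy volunteers" and continues: "The study will be comprised of two treatment sequences with a two-week washout period". The caption of Table-1 agrees: "Two Treatment Sequence, Open Labeled, Cross-Over Study Design for the Pharmacokinetic DDI-Study of Voriconazole with Clarithromycin".

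The column headings of Table-1 read "Treatment-1 Group-I (n= 12" and "Treatment-2 Group- II (n = 12" (closing brackets omitted). The first row, labelled Sequence-1, gives voriconazole alone to Group-I and the combination to Group-II. A washout row follows, then a second line of headings with the two treatment labels exchanged. The last row, labelled Sequence-2, gives the combination to Group-I and voriconazole alone to Group-II. No total sample size is stated.

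On analysis, Step-3 says only: "Appropriate statistical tests like t-test and analysis of variance (ANOVA) will be performed". It lists no model terms and does not say whether the t-test is paired.

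**The concern.** In a two-period crossover, a sequence is the order in which one subject receives the treatments, and the washout lies between that subject's two periods. Table-1 gives the name 'sequence' to rows that each contain both groups and that are separated by the washout.

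Taken at face value, this could mislead in three ways:

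- **Design.** Each 'sequence' would set one group against another, with no washout between its two treatments.
- **Sample size.** If the columns were periods and 12 were the number dosed in each, the trial would have 12 subjects, not 24.
- **Analysis.** An analyst coding factors from the table could enter a sequence term that is really period. Comparing the columns within one row would turn the crossover into a parallel comparison of 12 against 12 and lose the within-subject precision.

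**Working it through.** **1. Which reading fits the table?** Let V be voriconazole alone and VC the combination.

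| | Group-I (n = 12) | Group-II (n = 12) |
|---|---|---|
| Row 'Sequence-1' | V | VC |
| Washout | | |
| Row 'Sequence-2' | VC | V |

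- *Rows as periods, columns as sequences.* Group-I follows V then VC, and Group-II follows VC then V. The washout lies between each subject's two treatments. The exchanged treatment headings match the cells below them. Text, caption, group names and washout row all agree.
- *Row labels literal, columns as periods.* The orders are still V then VC and VC then V, but no washout separates a subject's two treatments, the washout row has no function, and 'Group-I' and 'Group-II' would have to name periods.

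Only the first reading uses every element of the table.

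**2. Sample size.** The plan gives no alpha, power, effect size or variance, so the 12 per group cannot be reproduced from a calculation. By head count: 12 + 12 = 24 subjects, 24 × 2 = 48 profiles, residual df 24 − 2 = 22. Correct labels would give the same numbers.

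**3. Washout.** Two weeks is 14 × 24 = 336 h. The Introduction says the voriconazole half-life "ranged from 8hr to 15hr": 336/15 = 22.4 and 336/8 = 42 half-lives. Its length is not in question here.

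**4. Does the row's name affect the treatment estimate?** Let d be a subject's second-row value minus first-row value on the log scale, π the row effect and τ the effect of adding clarithromycin. With no carryover:

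- Group-I: E(d) = π + τ
- Group-II: E(d) = π − τ
- so τ is estimated by (mean d in Group-I − mean d in Group-II)/2.

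The row effect cancels whether it is called period or sequence. The true sequence effect is constant within a subject and drops out of d. With within-subject SD s, Var(d) = 2s², so Var(τ̂) = ¼ × (2s²/12 + 2s²/12) = s²/12 and SE = s√(2/24).

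A simulated data set of 24 subjects (log-scale SDs 0.5 between and 0.3 within subjects) was fitted three ways:

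| Model | Estimate | SE | Residual df |
|---|---|---|---|
| subject + row + treatment | 0.240 | 0.066 | 22 |
| group + row + treatment, subject omitted | 0.240 | 0.171 | 44 |
| subject nested in row, + treatment | saturated | – | 0 (rank 48 of 48) |

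The nested coding leaves no residual degrees of freedom, so it fails visibly and does not mislead in silence. Omitting subject is costly, but that is a failure to analyse a crossover as one, and the row label does not cause it.

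**5. What the unlikely N = 12 reading would cost.** The 90% confidence factor on the ratio is exp[t(0.95, N−2) × s × √(2/N)], with s = √ln(1 + CV²). Power is for a true ratio of 1.25 at two-sided 0.05 (noncentral t). The CVs and the ratio are assumptions; the documents give none.

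| Within-subject CV | N = 24: factor, power | N = 12: factor, power |
|---|---|---|
| 20% | 1.10, 96% | 1.16, 70% |
| 30% | 1.16, 71% | 1.24, 39% |
| 40% | 1.21, 48% | 1.33, 25% |
| 50% | 1.26, 35% | 1.42, 18% |

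**6. A within-row comparison of 12 against 12.** With a within-subject CV of 30%, an assumed between-subject CV of 70% and a true ratio of 1.25, the log-scale power is 12%, against 71% for the crossover. On the raw scale, an unpaired t-test has about 10% and a paired t-test about 55%. The log-scale 71% should not be set against the raw-scale 10%. The loss is real on either scale, but the plan proposes no such comparison.

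**The case for a change.** The strongest case for acting is that Table-1 is the only place where the allocation is set out, and Step-3 names no factors and does not say the t-test is paired. Nothing later in the plan would therefore correct someone who coded from the table. The headings also mix group, treatment and sequence labels, the text is legible enough that extraction damage is an unlikely explanation, and relabelling would cost almost nothing.

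Part of this stands: the row labels are wrong, the total is left to addition, and the model terms are unwritten. The predicted harm does not follow from the label, however. It needs an analyst to take a study described twice as a crossover, ignore the group columns, and either drop the pairing or test a single row. The open wording on ANOVA belongs to Step-3 and would be just as open under a perfectly labelled table. Sequence, subject within sequence, period and treatment are the usual terms for this design, and an analyst would be expected to supply them.

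**Conclusion.** No change to the plan is needed. Table-1 misnames its periods as sequences, which is a clerical slip. Read by group, it sets out a valid two-sequence, two-period crossover with the washout in the right place and 12 + 12 = 24 subjects. Correct labels would leave every subject's treatments, the 48 profiles, the 22 residual degrees of freedom and the treatment estimate unchanged.

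This rests on reading Group-I and Group-II as separate sets of 12 volunteers, which the headings and the washout row both support, and on the declared crossover being analysed with subject in the model. The figures for N = 12 and for a within-row comparison show only the cost of misreading the table, under assumed CVs; they are not expected losses under the plan. Tidying the labels would help a reader but would not alter what the trial does or concludes.
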